#### 4.5.10.5 Serum Biomarker (Prior to *Futility Interim Analysis Only*)

Blood samples for analysis of Serum MIC-1 will be collected up until only the *futility* interim analysis. These samples may also be evaluated for the presence of candidate biomarkers of the proposed mechanism of action of idasanutlin. Exploratory assessments may include, but are not limited to, markers of cell death and apoptosis, circulating microRNA, as well as exploratory studies of circulating tumor specific DNA.

#### 4.5.10.6 Bone Marrow

Bone marrow samples will be collected to evaluate candidate biomarkers related to MDM2 and/or p53 pathways as well as other biomarkers related to treatment response, dose response or re-treatment. Evaluations may include proteomic tests, gene expression analyses, and nucleic acid sequencing of mechanism or disease-related markers.

Bone marrow (i.e., aspirate and, if sampled, bone marrow biopsy for the analysis of biomarkers) will be collected at screening. Bone marrow aspirate will be collected each time that bone marrow is required for HMRA (see [Appendix 1](#), [Appendix 2](#), [Appendix 4](#), and Section 4.5.8). If an unscheduled bone marrow aspirate is being collected to assess disease state, then additional bone marrow aspirate should be collected for flow and biomarker analyses. Procedures are described in detail in the Laboratory Manual(s).

- **Bone marrow for MRD flow cytometry:** analysis will include determination of abnormal cell phenotypes by flow cytometry.

After screening, the bone marrow for MRD flow cytometry is the priority sample.

- **EDTA bone marrow:** analysis to include, but not be limited to, sequencing of *TP53* and genes in MDM2 and p53 pathways, and analysis of gene mutations, rearrangements, and fusions commonly seen in AML patients (potentially to be used for MRD monitoring).

Sample for DNA is the priority bone marrow sample at screening.

- **Paxgene bone marrow:** analysis to include, but not be limited to, gene expression analysis for predictive gene signature. MRD monitoring by measuring *WT-1* transcript levels *will be assessed prior to futility interim analysis*.

Bone marrow RNA is the last bone marrow sample at all timepoints.

For patients who proceed to transplant, pretransplant bone marrow samples for MRD and biomarkers should be obtained, when possible.

If sites do their own MRD assessments locally or collect mutational data, please provide this information in the eCRF.

In case a patient consents to optional exploratory research the remainder of the bone marrow sample(s) will be stored in the Roche Clinical Repository (RCR), (see Section 4.5.13.1) for up to 15 years after the date of final closure of the clinical database.

#### **4.5.11 Electrocardiograms**

Triplicate ECG recordings will be obtained at specified timepoints, as outlined in the Schedule of Assessments ([Appendix 1](#) and [Appendix 2](#)). Additional ECG recordings may be performed at unscheduled timepoints as clinically indicated. Please note that the time points of ECG recordings are matched to PK sampling time points and should be performed sequentially as indicated in Section 4.5.10.

All ECG recordings must be performed using a standard high-quality, high-fidelity digital electrocardiograph machine equipped with computer-based interval measurements. Lead placement should be as consistent as possible. ECG recordings must be performed after the patient has been resting in a supine position for at least 10 minutes. All ECGs are to be obtained prior to other procedures scheduled at that same time (e.g., vital sign measurements, blood draws). Circumstances that may induce changes in heart rate, including environmental distractions (e.g., television, radio, conversation) should be avoided during the pre-ECG resting period and during ECG recording.

For safety monitoring purposes, the investigator or designee must review, sign, and date all ECG tracings. Paper copies of ECG tracings will be kept as part of the patient's permanent study file at the site. The following should be recorded in the appropriate eCRF: ECG abnormality (including waveform), heart rate; PQ, PR, RR, QRS intervals; QT interval and corrected QTcF interval based on the machine readings of the individual ECG tracings. Any morphologic waveform changes or other ECG abnormalities must be documented on the eCRF.

If at a particular postdose timepoint the mean QTcF is > 500 ms and/or 60 ms longer than the baseline value, another ECG must be recorded, ideally within the next 5 minutes, and ECG monitoring should continue until QTcF has stabilized on two successive ECGs. The investigator should also evaluate the patient for potential concurrent risk factors (e.g., electrolyte abnormalities, co-medications known to prolong the QT interval, severe bradycardia) and provide this information to the eCRF. In case a patient presents with an episode of grade  $\geq 2$  supraventricular arrhythmia (atrial fibrillation, atrial flutter, sinus tachycardia, etc.), an unscheduled ECG should be recorded. Standard-of-care treatment may be instituted per the discretion of the

investigator. If a PK sample is not scheduled for that timepoint, an unscheduled PK sample should be obtained.

If at a particular postdose timepoint in Cycle 1 the mean QTcF is > 500 ms and/or 60 ms longer than the baseline value, then ECG assessments at time points as in Cycle 1 are to be repeated in all following cycles.

Allowed ECG sampling assessment windows are as follows:

- Predose assessment: within 2 hours prior to idasanutlin morning dosing
- Assessments end of cytarabine infusion: up to 10 minutes after infusion
- Assessments 6 hours after idasanutlin morning dosing:  $\pm 18$  minutes
- Assessments 24 hours (equivalent to Day 2 predose idasanutlin):  $\pm 2$  hours

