#### **4.5.2            Assessments during Treatment and Follow-Up**

All assessments must be performed as outlined in [Appendix 1](#), [Appendix 2](#), [Appendix 3](#). Assessments scheduled on the day of study medication administration should be performed prior to administration of study medication, unless otherwise noted in the schedule of assessments. All other assessments, including hematology and biochemistry assessments scheduled on non-study medication dosing days, should be performed on the day of the specified visit within a window of  $\pm 2$  days. Please see [Appendix 4](#) for a detailed description of bone marrow sampling for HMRA and biomarker assessments, and the underlying algorithm governing continuation of study medication into consolidation therapy.

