## Appendix 1 Schedule of Assessments (cont.)

**Table 1 Cycle 1 (cont.)**

- c* If a Chest CT is performed up to 28 days prior to study drug administration, a chest x-ray is not required.
- d* If performed within 72 hours before the first study drug administration, the assessment does not have to be repeated on the first day of Cycle 1.
- e* Vital signs include body temperature, systolic and diastolic blood pressure, pulse rate and respiratory rate. Body surface area will also be measured at screening.
- f* Time points:
  - Cycle 1, Days 1: predose idasanutlin, end of cytarabine infusion, 6, and 24 (equivalent to Day 2, predose) hours post dose idasanutlin (a.m.)
  - Cycle 1, Day 5: predose idasanutlin, end of cytarabine infusion and 6 hours post dose idasanutlin (a.m.)
- g* ePRO questionnaires scheduled for administration during a clinic visit should be completed prior to the performance of non-ePRO assessments and the administration of study medication. ePRO questionnaires need to be completed only once during each of the recovery periods D29-42 and D43-56, if applicable.
- h* If patient is eligible to continue with consolidation therapy, be aware that a maximum of 56 days *is* allowed for recovery between cycles.
- i* All hematology and biochemistry assessments may be performed up to 1 day prior to the scheduled timepoint. Results must be reviewed by the investigator (or designee) PRIOR to study drug administration.
- j* At screening, bone marrow examination will require biopsy if an aspirate is not evaluable to confirm the AML diagnosis. For HMRA during study, bone marrow aspirates are required, but bone marrow biopsies should be performed at the discretion of the investigator.
- k* Bone Marrow MRD/Flow, EDTA and Paxgene to be collected at same time as Bone Marrow for response assessment. If unscheduled bone marrow aspirate is being collected for hematologic response assessment, then Bone Marrow MRD/Flow, EDTA, and Paxgene samples should also be collected. If any MRD assessments are done locally, please record this information in the eCRF.
- l* At screening, the priorities for bone marrow samples are EDTA > MRDFlow > Paxgene. At subsequent timepoints the priorities are MRD/FLOW > EDTA > Paxgene.
- m* If clinical genotyping sample is missed on Day 1, sample can be collected at any point in the study.

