## Appendix 1 Schedule of Assessments (cont.)

**Table 2 Cycles 2 and 3**

Cycle Day	Cycles 2 and 3 (Consolidation)									
	Treatment Period Cycle—28 days									Only Applicable in Case of Incomplete Blood Count Recovery by D28 a
	1	2	3	4	5	8	15	22	28	29–56
Idasanutlin/ placebo Dosing	x	x	x	x	x					
Cytarabine Dosing	x	x	x	x	x					
Symptom Directed Physical Examination	x					x	x	x	x	x
Vital Signs b , Weight, ECOG	x					x	x	x	x	x
ECG c (repeated, in triplicate)	x	x								
Urinalysis	x									
ePRO Assessments d	x					x	x		x	x
Serum Pregnancy Test	x									
Concomitant Medication										x
Adverse Events and Serious Adverse Events										x
Biochemistry e	x	x				x	x	x	x	x (weekly blood counts, latest up to D56)
Hematology e	x	x				x	x	x	x	x (weekly blood counts, latest up to D56)

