## Appendix 1 Schedule of Assessments (cont.)

**Table 2 Cycles 2 and 3 (cont.)**

- c Time points:
  - Day 1: predose idasanutlin, end of cytarabine infusion, 6, and 24 (equivalent to Day 2, predose) hours post-dose idasanutlin (only if there is QT prolongation found in Cycle 1 measurements)
- d ePRO questionnaires scheduled for administration during a clinic visit should be completed prior to the performance of non-ePRO assessments and the administration of study medication. ePRO questionnaires need to be completed only once during the recovery period D29-56 if applicable.
- e All hematology and biochemistry assessments may be performed up to 1 day prior to the scheduled timepoint. Results must be reviewed by the investigator (or designee) PRIOR to study drug administration.
- f For HMRA during the study, bone marrow aspirates are required, but bone marrow biopsies should be performed at the discretion of the investigator.
- g The priorities for bone marrow sampling are MRD/Flow > EDTA > Paxgene.
- h Bone marrow MRD/Flow, EDTA, and Paxgene to be collected at same time as bone marrow for response assessment. If unscheduled bone marrow aspirate is being collected for hematologic response assessment, then bone marrow MRD/Flow, EDTA, and Paxgene samples should also be collected. If any MRD assessments are done locally, please record this information in the eCRF.
- i Collect whenever bone marrow is sampled for HMRA assessment.
- j In Cycle 2, required up to *futility* interim analysis OR after *futility* interim analysis; if patient does not proceed to Cycle 3, please see [Appendix 4](#) for additional details.
- k After *futility interim analysis*, sample should be collected for all patients regardless if bone marrow is being collected.

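### Appendix 1 Table 2 omits the Day 5 ECGs that Protocol Section 4.5.11 requires in Cycles 2 and 3 after marked QTcF prolongation in Cycle 1

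*Protocol*

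**What the plan says.** Protocol Section 4.5.11 (Electrocardiograms) sets a rule for patients with a marked QTcF signal. If mean QTcF at a postdose time point in Cycle 1 is above 500 ms and/or 60 ms over baseline, "then ECG assessments at time points as in Cycle 1 are to be repeated in all following cycles". The sentence does not limit this to Day 1.

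The Cycle 1 time points are in Appendix 1, Table 1. The ECG row is marked at screening and on Days 1, 2 and 5. Under the label for time points, footnote f lists four points running from Day 1 to Day 2 predose, and three more on Day 5 (predose, end of cytarabine infusion, 6 hours).

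Cycles 2 and 3 are in Appendix 1, Table 2. The ECG row ("repeated, in triplicate") is marked on Days 1 and 2 only. Footnote c lists "Day 1: predose idasanutlin, end of cytarabine infusion, 6, and 24 (equivalent to Day 2, predose) hours post-dose idasanutlin", to be done "only if there is QT prolongation found in Cycle 1 measurements", and has no Day 5 line. The dosing rows of the same table run from Day 1 to Day 5.

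Sites are sent to these tables. Section 4.5.2 begins "All assessments must be performed as outlined in" Appendix 1 and the other schedules, and Section 4.5.11 says "Triplicate ECG recordings will be obtained at specified timepoints, as outlined in the Schedule of Assessments".

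**The concern.** Footnote c is conditional on QT prolongation in Cycle 1, so it is evidently meant to carry out the rule in Section 4.5.11. It carries out only part of it. Both texts are mandatory, they require different sets of ECGs, and the protocol does not say which prevails.

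What is at stake is safety monitoring in patients who have already shown a marked QTcF signal. Day 5 matters pharmacologically. The idasanutlin half-life is about one day and Day 5 is treated as steady state (Section 1.2.2.1), while a three-day schedule did not reach steady state (Section 1.2.1.2). Low potassium and low magnesium were common on the drug (Section 5.1.1.5), and Section 4.5.11 names electrolyte abnormalities as a QT risk factor to check. The gap is clearest for a patient whose prolongation was seen only on Cycle 1 Day 5. The schedule repeats the Day 1–2 ECGs and has none on the day the signal appeared.

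**Working it through.** The plan states no figure to reproduce, so the check is a comparison of texts and a count.

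**1. Scheduled on-treatment time points**

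| Time point | Cycle 1 (Table 1, footnote f) | Cycles 2 and 3 (Table 2, footnote c) |
|---|---|---|
| Day 1 predose | yes | yes |
| Day 1 end of cytarabine infusion | yes | yes |
| Day 1, 6 h | yes | yes |
| 24 h (Day 2 predose) | yes | yes |
| Day 5 predose | yes | no |
| Day 5 end of cytarabine infusion | yes | no |
| Day 5, 6 h | yes | no |
| Total | 4 + 3 = 7 | 4 |

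Shortfall against Section 4.5.11: 7 − 4 = 3 per cycle. Over two consolidation cycles it is 2 × 3 = 6 of 2 × 7 = 14.

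**2. Where the trigger can fire.** The labelled postdose points in Cycle 1 are Day 1 end of infusion, 6 h and 24 h, and Day 5 end of infusion and 6 h: 3 + 2 = 5. Two of the five are on Day 5, and Table 2 repeats neither.

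**3. Is this damage to the text?** The Table 2 row and its footnote agree with each other on Days 1 and 2 only, so a lost table mark is unlikely. Nothing is redacted here.

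**4. Does PK matching explain it?** Section 4.5.11 says ECG time points are matched to PK sampling. In Cycles 2 and 3, Section 4.5.10.1 and Appendix 2 have no Day 1 PK sample, and they do have a Day 5 predose idasanutlin sample until the futility interim analysis. Table 2 nevertheless requires ECGs on Day 1 and none on Day 5, so matching does not account for the pattern.

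**5. How many patients.** Arm sizes are from SAP Section 3.1 (293 and 147) and design CR rates from Protocol Section 6.1 (0.323 and 0.16).

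- Complete responders: 293 × 0.323 + 147 × 0.16 = 94.6 + 23.5, about 118.2.
- Affected = 118.2 × share starting Cycle 2 × share meeting the trigger. Neither share is in the documents. I assume 25% to 75% and 1% to 10%.
- Low: 118.2 × 0.25 × 0.01 = 0.3.
- Middle: 118.2 × 0.50 × 0.05 = 3.0.
- High: 118.2 × 0.75 × 0.10 = 8.9.

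The CR rates were set for TP53 WT patients and are applied here to all 440. Patients in CRp or CRi who start consolidation would add to the count.

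**The case against.** The strongest reply is that there is no conflict. Section 4.5.11 speaks of time points, not days, and goes on to list four ECG windows (predose, end of infusion, 6 hours, 24 hours) that match the four in footnote c. On that reading footnote c applies the rule exactly. This does not hold up. The four items are timing tolerances for ECGs in general, and three of them apply equally on Day 5. Table 1 footnote f uses the time-point label for both days, and Section 4.5.11 has no Day 1 limit.

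A second reply is that the body text already orders the Day 5 ECGs. Footnote c gives no threshold for prolongation, so a site must go to Section 4.5.11 anyway and will find the repeat instruction there. That is fair as far as it goes: missed ECGs are a likely result of the table, not a certain one. It also concedes that the table is incomplete.

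A third reply concerns the stakes. Consolidation halves the idasanutlin dose (Section 4.3.2.4), and earlier data showed no correlation between drug concentration and QTcF (Section 1.2.2.2). Triggered patients keep the Day 1–2 triplicates and the repeat-until-stable rule. They also have an ECG at the completion/discontinuation visit (Appendix 1, Table 3), and Section 4.5.11 adds: "Additional ECG recordings may be performed at unscheduled timepoints as clinically indicated". All of this stands and keeps the point minor. Discretionary ECGs do not replace required ones.

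The patient count also deserves little weight. It spans about thirty-fold because two inputs are assumed. Only the count of 4 against 7 comes from the documents.

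**Conclusion.** The inconsistency is real as the documents are written. For patients meeting the Section 4.5.11 trigger, the Cycle 2 and 3 schedule carries 4 of the 7 required ECG time points and omits all three on Day 5. This rests on the plain reading of Section 4.5.11 together with Table 1 footnote f.

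Severity is minor. The number affected is small under any plausible assumption, and several backstops remain. OS, alpha, power, sample size and every planned efficacy analysis are untouched.

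**What to change.** In Appendix 1, Table 2, mark Day 5 in the ECG row. In footnote c, add a Day 5 line with the three Cycle 1 points (predose idasanutlin, end of cytarabine infusion, 6 hours after the morning idasanutlin dose). Apply it to patients who met the Section 4.5.11 threshold in Cycle 1. Leave footnote c's existing, broader condition for the Day 1–2 ECGs as it is, so that no current monitoring is lost.

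The cost is one table mark and one footnote line. The ECGs number at most 3 time points × 3 tracings = 9 per consolidation cycle, or 18 over Cycles 2 and 3. They fall only on triggered patients, on a day when they already receive intravenous cytarabine. Section 4.5.11 already requires these ECGs, so no new procedure is introduced. If the sponsor meant Days 1–2 only, Section 4.5.11 must say so; one of the two texts has to change.

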#### **4.5.12 Patient-Reported Outcomes**

PRO data will be collected via electronic questionnaires to more fully characterize the clinical profile of idasanutlin. The questionnaires will be translated as required in the local language. To ensure instrument validity and that data standards meet health authority requirements, questionnaires scheduled for administration during a clinic visit should be completed prior to the performance of non-PRO assessments and the administration of study medication.

The EORTC QLQ-C30 is a validated and reliable self-reporting measure (Fayers et al. 2001) consisting of 30 questions incorporated into five functional scales (physical, role, cognitive, emotional, and social), three symptom scales (fatigue, pain, nausea, and vomiting), and a global health status/global quality-of-life scale. The remaining single items (dyspnea, appetite loss, sleep disturbance, constipation, and diarrhea) assess the additional symptoms experienced by patients with cancer and the perceived financial burden of treatment. The EORTC QLQ-C30 questionnaire takes 5 minutes to complete. The EORTC QLQ-C30 will be conducted using electronic patient-reported outcome (ePRO) prior to treatment across all cycles on Days 1, 8, 15, and 28, and between Days 29–56, if applicable. Additionally, the EORTC QLQ-C30 will be collected during study drug completion/discontinuation visit and every 3 months until relapse during long-term follow-up of patients in clinical remission. An additional EORTC QLQ-C30 questionnaire must also be completed after progressive disease (PD).

The EQ-5D-5L is a self-report health status questionnaire that consists of six questions used to calculate a health utility score for use in health economic analysis (EuroQol Group 1990; Brooks 1996; Herdman et al. 2011; Janssen et al. 2013). There are two components to the EQ-5D-5L: a five-item health state profile that assesses mobility, self-care, usual activities, pain/discomfort, and anxiety/depression, as well as a visual analogue scale that measures overall health state. Published weighting systems allow for creation of a single summary score. Overall scores range from 0 to 1, with low scores representing a higher level of dysfunction. The EQ-5D-5L questionnaire takes

5 minutes or less to complete, and assessments are made at the same time as the EORTC QLQ-C30. An additional EQ-5D-5L questionnaire is also required to be completed after PD.

Patients will use an ePRO device to capture PRO data for the above two 5-minute surveys. The ePRO device and/or instructions for completing the PRO questionnaires electronically will be provided by the investigator staff. The data will be transmitted via transmission method (wireless daily) automatically to a centralized database at the ePRO vendor. The data can be accessed by appropriate study personnel securely via the Internet.

#### **4.5.13 Samples for Roche Clinical Repository**

##### **4.5.13.1 Overview of the Roche Clinical Repository**

The RCR is a centrally administered group of facilities used for the long-term storage of human biologic specimens, including body fluids, solid tissues, and derivatives thereof (e.g., DNA, RNA, proteins, peptides). The collection and analysis of RCR specimens will facilitate the rational design of new pharmaceutical agents and the development of diagnostic tests, which may allow for individualized drug therapy for patients in the future.

Specimens for the RCR will be collected from patients who give specific consent to participate in this optional research. RCR specimens will be used to achieve the following objectives:

- To study the association of biomarkers with efficacy, adverse events, or disease progression
- To increase knowledge and understanding of disease biology
- To study drug response, including drug effects and the processes of drug absorption and disposition
- To develop biomarker or diagnostic assays and establish the performance characteristics of these assays

##### **4.5.13.2 Approval by the Institutional Review Board or Ethics Committee**

Collection and submission of biological samples to the RCR is contingent upon the review and approval of the exploratory research and the RCR portion of the Informed Consent Form by each site's Institutional Review Board or Ethics Committee (IRB/EC) and, if applicable, an appropriate regulatory body. If a site has not been granted approval for RCR sampling, this section of the protocol (Section 4.5.13) will not be applicable at that site.

#### **4.5.13.3 Sample Collection**

If RCR consent is provided, any mandatory bone marrow material (cells, RNA, and DNA) remaining after protocol defined analysis will be stored for up to 15 years in the RCR.

The following samples will be collected for identification of dynamic (non-inherited) biomarkers:

- Blood for serum isolation on Day 1, Day 5, and at disease relapse (in those patients who have hematological response).
- Blood for plasma isolation on Day 1, Day 5, and at disease relapse (in those patients who have hematological response).

The following samples will be collected for identification of genetic (inherited) biomarkers:

- Blood for DNA isolation will be collected on Day 1. If the sample is missed on Day 1, it can be collected at any time in the study.

For all samples, dates of consent should be recorded on the associated RCR page of the eCRF. For sampling procedures, storage conditions, and shipment instructions, see the Laboratory Manual.

RCR specimens will be destroyed no later than 15 years after the date of final closure of the associated clinical database. The RCR storage period will be in accordance with the IRB/EC-approved Informed Consent Form and applicable laws (e.g., health authority requirements).

The dynamic biomarker specimens will be subject to the confidentiality standards described in Section 8.4. The genetic biomarker specimens will undergo additional processes to ensure confidentiality, as described below.

